4.8.1. Handling of products used in the study

At study sites, the test drug must be stored in a refrigerator at 2 to 8°C in a place that may only be accessed by the Principal Investigator, co-investigators and an authorized administrative representative of the healthcare facility, who is provided with access according to local rules.

The product may be stored only at the official study site involved in this study. The Investigator must ensure safe product storage, preventing its loss, theft or inappropriate storage conditions (temperature) required by the Sponsor and specified in the Investigator's Brochure. The Investigator is required to keep a temperature log.

4.9. Study numbers storage and unblinding procedure

The drug will be used in an open-label mode so the unblinding procedure is not envisaged.

4.10. List of all data recorded directly in the CRF (i.e., without prior written or electronic entry) and regarded as source data

All data that must be recorded in the CRF must be present in the source documents of the study site.

Data that is not subject to registration in the source documents should not be included in the CRF.

5. SELECTION AND EXCLUSION OF STUDY PARTICIPANTS

5.1. Inclusion criteria

1. Signed informed consent;
2. Male;
3. Age 18 - 45 years inclusive;
4. Body mass index (BMI) within normal limits (18.5 - 30.0 kg/m²);
5. A verified diagnosis of "healthy", established according to the medical history, physical examination and laboratory data:

Translated from Russian to English, dated 06-Jul-2020

- absence in the history and at the time of the screening examination of clinically obvious impaired function of the cardiovascular, respiratory, nervous, hematopoietic, endocrine, gastrointestinal systems, liver and kidneys;
 - absence of history of cardiovascular diseases;
 - complete blood count, blood chemistry, and urinalysis results are within reference ranges adopted at the study site;
 - hemodynamic parameters within normal limits: SBP - within 100 - 120 mm Hg., DBP - within 60 - 80 mm Hg. Art., heart rate - 50 - 90 bpm;
 - absence of chronic infections (tuberculosis) or history of chronic inflammatory diseases;
 - absence of laboratory markers of hepatitis B, C, HIV and syphilis;
 - absence of acute infectious diseases within 4 weeks before inclusion in the study;
 - absence of mental disorders and any other conditions that can affect the ability of the participant to follow the requirements of the protocol, including depression;
 - satisfactory well-being (in the opinion of the volunteer) within 30 days before signing of the informed consent form;
6. Absence of evidence of alcohol abuse or drug addiction at the time of inclusion in the study or in medical history, as well as negative results at the screening alcohol breath test, together with a negative result of the urine drug test;
7. The ability of the volunteer to follow the Protocol procedures, in the Investigator's opinion;
8. The willingness of volunteers and their sexual partners of childbearing potential to use reliable methods of contraception, starting 2 weeks before inclusion in the study and throughout the study (day of injection and 70 days from the date of its administration). This requirement does not apply to participants who underwent surgical sterilization. Reliable methods of contraception involve the use of 1 barrier method in combination with one of the following: spermicides, intrauterine device/oral contraceptives for the sexual partner;
9. Willingness not to drink alcohol within 24 hours before the administration of the test product and for 8 days after.

Translated from Russian to English, dated 06-Jul-2020

1.2. Exclusion criteria

1. A history of use of monoclonal antibody products against interleukin-6 or its receptor;
2. Allergy history (anaphylactic shock or multidrug allergy);
3. Known allergy or intolerance to monoclonal antibody drugs (murine, chimeric, humanized, or human) or any other components of the study drug.
4. Major surgery less than within 30 days prior to signing the informed consent form;
5. Severe infections (including those that required hospitalization or parenteral antimicrobial/antimycotic/antiviral/antiprotozoal treatment) within 6 months before signing the ICF;
6. Systemic antimicrobial/antimycotic/antiviral/antiprotozoal treatments within 2 months before signing the ICF;
7. More than 4 episodes of respiratory infections within 6 months before signing the informed consent form;
8. Impossibility to insert a venous catheter for blood sampling (for example, due to skin diseases at venipuncture sites);
9. Diseases or other conditions that can affect the pharmacokinetics of the test product (e.g., chronic liver, kidney, blood, cardiovascular, bronchopulmonary and neuroendocrine systems disorders (including diabetes mellitus) etc.);
10. A history of fever above 40°C;
11. A history of episodes of elevated hepatic transaminases above 2.5 x ULN;
12. Epileptic seizures, history of seizures;
13. Current depression or a history of depression, suicidal thoughts/attempts at the time of the screening examination or a history of such behavior;
14. Regular use of any oral or parenteral medications, including over-the-counter drugs, vitamins, and dietary supplements within less than 2 weeks before signing the informed consent;
15. Use of medications, including OTC drugs that have a pronounced effect on hemodynamics, liver function, etc. (barbiturates, omeprazole, cimetidine, etc.) within less than 30 days before signing the informed consent form;
16. Use of medicinal products that affect the immune status (cytokines and their inducers, glucocorticoid hormones, etc.) within less than 2 months prior to signing the informed consent form;

Translated from Russian to English, dated 06-Jul-2020

17. Vaccination within 4 weeks prior to signing of informed consent form;
18. Values of standard laboratory tests and investigations results that are beyond the reference ranges;
19. Smoking more than 10 cigarettes per day;
20. Consumption of more than 10 units of alcohol per week (1 unit of alcohol is equivalent to ½ liter of beer, 200 mL of wine or 50 mL of liquor) or a history of alcoholism, drug addiction or drug abuse;
21. Donation of 450 mL or more of blood or plasma within 2 months prior to signing of the informed consent form;
22. Participation in other clinical studies within less than 2 months before signing the informed consent form or simultaneous participation in other clinical studies;
23. Prior participation in this clinical study.

5.3. Exclusion criteria

Volunteers will be excluded from further participation in the study in the following cases:

1. Identification, after the volunteer's inclusion in the study, of gross violations of inclusion/non-inclusion criteria (as decided by JSC BIOCAD);
2. Patient's withdrawal of the consent to participate in the study;
3. AEs and SAEs, laboratory abnormalities or concomitant diseases, when, in the opinion of the investigator or Sponsor, the continuation of the study treatment is impossible or dangerous for the volunteer, or is not in the best interests of the volunteer, or is unsafe;
4. The volunteer misses more than 1 doses of BCD-089 (in this case, the withdrawal of such a patient will have to be agreed with representatives of JSC BIOCAD);
5. The patient has a major depressive disorder or suicidal ideation or makes suicidal attempts;
6. If the study is terminated by the decision of JSC BIOCAD, local Ethics Committee, or regulatory bodies;
7. In case of the use of drugs prohibited by the Protocol;
8. In case of the volunteer's death.

Translated from Russian to English, dated 06-Jul-2020

The investigator had to inform JSC BIOCAD about his premature withdrawal and the reasons of premature withdrawal within 24 hours.

5.3.1. Substitution of volunteers who withdrew from the study

The volunteers can be substituted in the following cases:

1. Volunteers who withdrew the study for reasons not related to administration of the study drug (missing visit, withdrawal of consent, systematic violation of visit windows, etc.).
2. Non-compliant volunteers (see Section 6.6).

Volunteers who withdrew from the study after administration of the study drug for safety reasons (AE that did not allow to come to a visit to perform the Protocol procedures) will not be replaced.

5.4. Follow-up of subjects who withdrew from the study

Follow-up of volunteers who received at least one dose of the drug

In case of early withdrawal of a volunteer after administration of the study drug, it is required to conduct an “Early Withdrawal Visit” and fill out an “Early Withdrawal Form”.

If a patient is discontinued from the study due to an AE/SAE, the Investigator should continue his/her management and follow-up after the “Early Withdrawal Visit” in accordance with the standard practices used at the study site for AE/SAE treatment. The volunteer will be followed up until full resolution of the AE or SAE.

6. USE OF THE TEST DRUG

6.1. Dosing regimen tested

Study No. BCD-089-1 includes seven cohorts:

1. Cohort 01 - 1 volunteer to whom a single subcutaneous injection of BCD-089 at a dose of 0.06 mg/kg will be administered.

Translated from Russian to English, dated 06-Jul-2020

2. Cohort 02 - a maximum of 6 volunteers to whom a single subcutaneous injection of BCD-089 at a dose of 0.3 mg/kg will be administered.
3. Cohort 03 - a maximum of 6 volunteers to whom a single subcutaneous injection of BCD-089 at a dose of 0.625 mg/kg will be administered.
4. Cohort 04 - a maximum of 6 volunteers to whom a single subcutaneous injection of BCD-089 at a dose of 1.0 mg/kg will be administered.
5. Cohort 05 - a maximum of 6 volunteers to whom a single subcutaneous injection of BCD-089 at a dose of 1.6 mg/kg will be administered.
6. Cohort 06 - a maximum of 6 volunteers to whom a single subcutaneous injection of BCD-089 at a dose of 2.2 mg/kg will be administered.
7. Cohort 07 - a maximum of 6 volunteers to whom a single subcutaneous injection of BCD-089 at a dose of 2.9 mg/kg will be administered.

The inclusion of volunteers in the study is sequential. The first to participate in the study is one volunteer, representing the cohort “01”, who is administered a single subcutaneous injection of the estimated maximum safe dose of BCD-089 - 0.06 mg/kg. In the absence of grade 3-4 adverse events related to the test product, developing within the first 7 days after the injection, three volunteers are included in cohort 02. Further, the volunteer inclusion algorithm corresponds to the following general principle:

In the absence of any grade 3-4 AEs (DLT) associated with the test product within 7 days after the injection, the next cohort of three volunteers with dose escalation is included in the study - cohort 02 (cohort 03, cohort 04, etc.).

If grade 3-4 AEs (DLT) associated with the test product were recorded in only one volunteer in a cohort of three volunteers, three more healthy volunteers will be additionally included in this cohort.

With the development of grade 3-4 AEs (DLT) associated with the test product in two of six volunteers, the dose at which this event was recorded will be taken as the maximum tolerated dose, further dose escalation will be ceased.

6.2. Investigational product dose correction

Not planned.

Translated from Russian to English, dated 06-Jul-2020

6.3. Overdose

[REDACTED]

6.4. Concomitant therapy, allowed and prohibited medications

In the course of the study, the volunteers must not use any additional medicinal products (besides those specified in the study design).

In this study, there are no specific restrictions on medications for intercurrent diseases and conditions that a volunteer might have during the study period. In case of disorders that occur during the study, the volunteers can receive full supportive care in accordance with standard guidelines.

6.5. Methods of monitoring adherence to study procedures

Information about drug administration, doses, and between-visit intervals will be documented during the study.

Clinical Studies Specialist will review the accountability documents during monitoring visits and at the end of the study.

6.6. Compliance assessment

In this clinical study, any volunteer is considered to be non-compliant if he:

- Missed more than one visit;
- Deviated from the scheduled window for more than one visit;
- Missed sampling of more than 2 blood samples for evaluation of pharmacokinetics and pharmacodynamics;
- Deviated from the scheduled window for pharmacokinetic and pharmacodynamic sampling by a time exceeding the acceptable deviation described in Tables 3 and 4.

Translated from Russian to English, dated 06-Jul-2020

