	
5. Cohort 05 - a maximum of 6 volunteers to whom a single subcutaneous injection of BCD-089 at a dose of 1.6 mg/kg will be administered.
 
6. Cohort 06 - a maximum of 6 volunteers to whom a single subcutaneous injection of BCD-089 at a dose of 2.2 mg/kg will be administered.
 
7. Cohort 07 - a maximum of 6 volunteers to whom a single subcutaneous injection of BCD-089 at a dose of 2.9 mg/kg will be administered.

Time points for PK blood sampling
	
[REDACTED]
 
16. [REDACTED]

Time points for blood sampling for CRP, IL-6 and soluble IL-6 receptor testing
	
[REDACTED]
 
16. [REDACTED]

Translated from Russian to English, dated 06-Jul-2020

Time points for blood sampling for membrane receptor occupancy assay for BCD-089
	
[REDACTED]
 
5. [REDACTED]

Planned sample size:
	
Up to 37 healthy volunteers.

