9. STATISTICAL METHODS

9.1 Calculation of the parameters of pharmacokinetics and pharmacodynamics

9.1.1. Pharmacokinetic parameters

Based on the calculated concentration values for the anti-IL-6 monoclonal antibody in the blood of each volunteer, the following pharmacokinetic variables will be estimated at time points specified in this protocol:

1. C_{\max} - maximum serum concentration of anti-IL-6 receptor antibody over the observation period.
2. t_{\max} - time to achieve maximum serum concentration (C_{\max}) of anti-IL-6 receptor antibody.
3. AUC_{0-1680} — the area under the concentration of anti-IL-6 receptor monoclonal antibody-time curve over the time interval from 0 to 1680 hours. AUC_{0-1680} will be calculated using the trapezoid method using the following formula, where C_p is the concentration of the drug BCD-089 in the blood at the time t_p in hours:

$$t_p \in \{0; 2; 8; 12; 24; 48; 72; 96; 120; 168; 240; 336; 504; 672; 1176; 1680\}_{p=1, \dots, 16}$$

4. $AUMC_{0-1680}$ - total area under the curve of the concentration of anti-IL-6 receptor monoclonal antibody multiplied by time over the time interval from 0 to 1680 hours. $AUMC_{0-1680}$ will be calculated using the following formula:

$$AUMC_{0-1680} = \sum_{p=2}^{16} \frac{(C_p * t_p + C_{p-1} * t_{p-1}) * (t_p - t_{p-1})}{2},$$

where C_p — concentration of anti – IL – 6

– receptor monoclonal antibody против рецептора ИЛ6

Translated from Russian to English, dated 06-Jul-2020

in the blood at t_p

$$t_p \in \{0; 2; 8; 12; 24; 48; 72; 96; 120; 168; 240; 336; 504; 672; 1176; 1680\}_{p=1, \dots, 16}$$

5. **Total clearance (Cl)** is a parameter that reflects the volume of test tissue, which is cleared from the anti-IL-6 receptor monoclonal antibody per unit of time and is determined by the ratio of the anti-IL-6 receptor monoclonal antibody dose (*DOSE*) to $AUC_{(0-1680)}$:

$$CL = \frac{DOSE}{AUC_{0-1680}}$$

6. **Mean residence time (MRT)** of the anti-IL-6 receptor monoclonal antibody molecule in the body will be calculated as the ratio of $AUMC_{0-1680}$ to AUC_{0-1680} :

$$MRT = \frac{AUMC_{0-1680}}{AUC_{0-1680}}$$

7. **Elimination constant** of the anti-IL-6 receptor monoclonal antibody (k_{el}) will be determined using the following formula:

$$k_{el} = \frac{1}{MRT}$$

8. **Half-life period** of the anti-IL-6 receptor monoclonal antibody ($T_{1/2}$) will be determined using the following formula:

$$T_{1/2} = \frac{\ln(2)}{k_{el}} = \ln(2) * MRT$$

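### Section 6.6 sets no count for out-of-window PK/PD draws, so one late draw can make a dosed volunteer replaceable; AUC uses nominal times, and the maxima of 1, 6 and 37 allow for no replacements

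*Combined protocol and SAP*

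**What the plan says.** **Compliance (6.6).** Three of the four bullets carry a count. Missed visits need more than one. For visit windows the wording is "Deviated from the scheduled window for more than one visit", and for missed samples "Missed sampling of more than 2 blood samples for evaluation of pharmacokinetics and pharmacodynamics". The fourth bullet, on sampling windows, reads "Deviated from the scheduled window for pharmacokinetic and pharmacodynamic sampling by a time exceeding the acceptable deviation described in Tables 3 and 4". It has a tolerance in time but none in number.

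**Replacement (5.3.1).** The list opens "The volunteers can be substituted in the following cases", and its second item is "Non-compliant volunteers (see Section 6.6". No cap is given. The only group barred from replacement is "Volunteers who withdrew from the study after administration of the study drug for safety reasons".

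**Sample size (Synopsis; 9.2, sample-size rationale).** The total is "Up to 37 healthy volunteers". The table has a mandatory column and a column for additions after a DLT, and no column for replacements. Cohort 01 has one volunteer and no additions.

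**AUC (9.1.1, 9.1.2).** In 9.1.1, C_p "is the concentration of the drug BCD-089 in the blood at the time" t_p, and t_p is taken from a list of 16 fixed hours from 0 to 1680. Section 9.1.2 uses the same list for CRP, IL-6 and soluble IL-6 receptor.

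**Analysis sets and deviations (9.7, 11.2).** Section 9.7 admits a volunteer to the PK and PD analyses with up to two missing samples and sets no out-of-window criterion. Section 11.2 lists two or more missed PK/PD samples as an example of a probable major deviation, and requires any volunteer with a major deviation to be left out of the final PK/PD analysis.

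**The concern.** A sample drawn late still carries information, and a sample never drawn carries none. As 6.6 is written, the late one alone can make the volunteer non-compliant, while two absent ones cannot. A volunteer can therefore become replaceable under 6.6 and 5.3.1 while 9.7 keeps his data in the PK analysis.

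Two things are at stake. First, nearly all draws follow the injection, so replacement generally means dosing another healthy volunteer in a first-in-human study, possibly because of one late tube. Secondly, the primary AUC assigns a late concentration to a time at which it was not measured.

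The counts also interact with escalation. The 3+3 rules speak of three and of six volunteers. They do not say how a volunteer who was dosed and then replaced counts for DLT. Six of the 16 sampling times (240, 336, 504, 672, 1176 and 1680 h) fall after the 7-day DLT window, so a replacement can be triggered after the next cohort has begun.

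**Working it through.** **1. The stated total.** From the sample-size table: mandatory 1 + 6 × 3 = 19; DLT additions 0 + 6 × 3 = 18; total 19 + 18 = 37 = 1 + 6 × 6. The figure reproduces exactly and leaves no place for a replacement.

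**2. When the maxima are passed.**
- Cohort 01: 1 + 1 replacement = 2, against a stated 1. No DLT is needed.
- A later cohort not expanded: 3 + 1 = 4, within 6.
- A later cohort expanded after a DLT: 6 + 1 = 7, against a stated 6.
- Whole study: with k expanded cohorts and r replacements, the number dosed is 19 + 3k + r. Passing 37 needs r of at least 19 − 3k, which is 19 replacements with no expansion and 10 with three expansions.

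**3. How often the sampling-window bullet would apply.** The per-draw rate q is an assumption, because the documents give none and the windows of Tables 3 and 4 are not visible. With 16 coinciding and independent PK/PD draws:
- P(at least one late) = 1 − (1 − q)^16
- P(more than two late) = P(X ≥ 3), X binomial(16, q)

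| q | At least one late | Expected among 19 | More than two late |
|---|---|---|---|
| 0.5% | 8% | 1.5 | 0.01% |
| 1% | 15% | 2.8 | 0.05% |
| 2% | 28% | 5.2 | 0.4% |
| 3% | 39% | 7.3 | 1.1% |

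The expected number is 19 × P(at least one late), for example 19 × 0.386 = 7.3.

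**4. Effect of nominal times on AUC.** Take the linear trapezoid written out in 9.1.2. If an interior sample is drawn δ hours late, the two terms containing t_p change, and AUC at actual times minus AUC at nominal times is δ(C_p + C_{p−1})/2 − δ(C_{p+1} + C_p)/2 = δ(C_{p−1} − C_{p+1})/2. For a late draw, nominal times therefore overstate AUC where the curve is rising and understate it where it is falling. The documents give neither concentrations nor visible windows, so the error cannot be put in figures. At actual times it does not arise.

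**5. Two missed samples, section by section.** Section 6.6: compliant. Section 9.7: eligible for the PK and PD analyses. Section 11.2: probable major deviation, with exclusion from the final PK/PD analysis. The three cannot all be applied.

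**The case against.** The strongest reply is that nothing here forces an extra dosing. Replacement is permitted, not required. Section 5.3.1 is headed as covering volunteers who withdrew, and non-compliance under 6.6 is not itself a withdrawal criterion in 4.7 or 5.3. The missing count may be an oversight. The bullet does carry a time tolerance, and its strictness cannot be judged because the windows are not visible. All of this stands. It makes the one-draw reading literal rather than explicit, which is a reason to state a number.

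Several stronger readings are tempting, and the documents do not support them:
- A reader might infer that the stated maximum is wrong whenever 5.3.1 is used. It is not: one replacement in an unexpanded cohort of 3 gives 4, within 6.
- A reader might project 37 plus first-round replacements, 37 + 2.9 to 37 + 14.3, or about 40 to 51 dosed. That needs all six later cohorts expanded. Cohorts 02 to 06 must each have exactly one DLT in three and then none in three, which has probability at most 3(1/6)(5/6)^5 = 0.201, and cohort 07 exactly one in three, at most 0.444. The product 0.201^5 × 0.444 is about 0.015%, whatever the DLT rates.
- A reader might say that two missed samples are simply tolerated. That holds for 6.6 and 9.7 only.
- A reader might fear that a replaced volunteer drops out of the safety analysis. Section 9.7 already keeps everyone who received the drug. Only the DLT count is unstated.
- A reader might suppose that nominal times are the reason for the strict bullet. No section links the two.

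The assumed rate is also crude. Time 0 is before the dose, and the draws to 24 h are taken while the volunteer stays at the site. Counting only the 15 later draws gives 1 − (1 − q)^15, or 7% to 37%, so the contrast in the table remains. Section 9.5 on missing and uncertain data is redacted and may say more about handling samples. It would not change the visible wording of 6.6, 5.3.1 or the sample-size table.

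**Conclusion.** The point holds as a gap in the rules, not as a forecast that the limits will be breached. Read literally, 6.6 treats one late draw more severely than two absent ones, and 5.3.1 makes that volunteer replaceable with no cap. The maxima of 1, 6 and 37 are not enforced by the rules: 2 dosed in cohort 01, or 7 in an expanded cohort, follow from a single permitted replacement.

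Passing 37 overall is very unlikely unless several cohorts expand and late draws are frequent. With no expansion it needs 19 replacements, against 1.5 to 7.3 expected if every non-compliant original volunteer is replaced once.

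The contrast between 8% to 39% and 0.01% to 1.1% rests on assumed, independent late-draw rates of 0.5% to 3% over 16 draws. The fixed nominal times in the primary AUC and the conflict between 6.6, 9.7 and 11.2 depend on no assumption. The changes are cheap and should be made.

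**What to change.** 1. In 9.1.1 and 9.1.2, define t_p as the actual elapsed time since injection, so that a late sample is used where it was taken.
2. In 6.6, give the sampling-window bullet a count, preferably one count covering samples missed or out of window together. Reconcile 6.6, 9.7 and 11.2 on a single threshold. Changing 6.6 alone would leave the conflict with 11.2.
3. In the Synopsis and 9.2, say whether replacements fall inside or outside the limits of 1, 6 and 37, and give a cap. Reconcile 5.3.1 with the escalation rules so that the protocol states how a volunteer who was dosed and then replaced is counted for DLT.

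The cost is protocol and analysis-plan wording. Actual sampling times must be carried into the PK/PD dataset, and the stated maximum may become slightly larger.
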